##### Wound Closure Procedure:

The wound closure will be performed at genuflex position.

For patients randomized to receive barbed sutures, the deep layer and the intermediate layer will be repaired and closed by using one [REDACTED] suture respectively. The

ratio of incision length to suture length for both layers is recommended to be no higher than 1:3. For patients randomized to receive conventional sutures, [REDACTED] sutures will be used to close the deep and the intermediate layers with interrupted suturing manner. Then for both groups, [REDACTED] sutures will be used to close the intradermal layer and the [REDACTED] Skin Closure System, a topical skin adhesive (TSA) will be applied to the skin surface to tissue approximation. Please find the details in Table 4,5.

**Table 4: Wound closure procedure and devices in barbed suture group**

Layer	Suture Material	Suture Technique	Code
Deep layer	[REDACTED]	Continuous	[REDACTED]
Intermediate layer	[REDACTED]	Continuous	[REDACTED]
Intradermal layer	[REDACTED]	Continuous	[REDACTED]
Skin layer	[REDACTED]	N/A	[REDACTED]

**Table 5: Wound closure procedure and devices in control group**

Layer	Suture Material	Suture Technique	Code
Deep layer	[REDACTED]	Interrupted	[REDACTED]
Intermediate layer	[REDACTED]	Interrupted	[REDACTED]
Intradermal layer	[REDACTED]	Continuous	[REDACTED]
Skin layer	[REDACTED]	N/A	[REDACTED]

The sutures and TSA will be used per the Instructions for Use [21-24]. Surgeons must be familiar with surgical procedures and techniques involving absorbable sutures as risk of wound dehiscence/separation may vary with the site of application and the suture material used. Consequently, surgeons must consider the in vivo performance when evaluating the eligibility of potential subjects for enrollment into the study. The use of an absorbable suture may be inappropriate in elderly, malnourished, or debilitated patients, or in patients suffering from conditions which may delay wound healing.

Postoperative Care:

Postoperative care will be performed per institutional requirements ROM exercises will be performed adhering to institutional requirements and specific guidelines regarding postoperative care. Patient status is monitored closely until discharge. Thrombolytic therapy beyond discharge can be continued prophylactically per intuition requirements or not. Changes in concomitant medications including analgesics will be recorded throughout inpatient stay.

Other – Health Economic Data Collection

In order to estimate the costs characteristics and influence factors, the following costs data will be collected if available:

Overall fee: Total fees, hospital stay fees, self-paid amount, etc  
 Comprehensive medical services costs, including general medical service charges, general treatment procedure fees, and nursing costs, etc.  
 Diagnosis fees, including pathological diagnosis fee, imaging diagnosis fee, clinical diagnosis fee, and laboratory diagnosis fee, etc.

Treatment fees, including non-operation treatment fee (clinical physical treatment fee), operation costs (anesthetic fee, procedure costs)  
Rehabilitation fee, including rehabilitation costs, etc.  
Medicines fee, including traditional Chinese medicine, western Chinese medicine, antibiotic fees, etc.  
Blood and blood products costs, including fees of blood, blood coagulation products, etc.  
Medical supplies costs, including fees of disposal medical supplies for examination, fees of disposal medical supplies for treatment, and disposal medical supplies for surgery, etc.  
The other costs, if applicable.

### **3.3.2 Blinding**

Blinding practices for this study will include the following:

**Patients:** Patients will be informed of the 1:1 randomization between the different suturing material and technique, but will remain blinded as to which implant they actually received until after they have completed all study follow-up.

**Implanting surgeon:** It is not possible to blind the implanting physician due to the different suturing technique and products.

**Medical Records:** All medical records (source documents) documenting the implant procedure through hospital discharge and all follow-ups will not be blinded because the devices used will be described in the operation record.

**Monitors:** Monitors will not be blinded because the detachable labels provided with the product identify the product and may be used in the study device accountability records and patient research file for the purpose of device accountability and source document validation.

### **3.3.3 Subject Compliance**

Study personnel will make preemptive contact with subjects as necessary to ensure compliance with the follow-up schedule.

## **3.4 Study Procedures**

### **Screening**

Subjects will be consented prior to any actual study-specific screening procedures being conducted. Subjects will be considered enrolled into the study upon satisfaction of the following criteria:

- Completion of the informed consent process and signing the ICD;
- Verification of the eligibility criteria (Sections 3.2) by the PI and authorized investigators. The verification must be conducted by the PI and/or authorized investigators prior to randomization.

### **Screening Failures**

Screened subjects who are not enrolled will be considered screen failures. For subjects who are determined to be screen failures, only the following data will be recorded on the eCRF:

- Informed consent date;

- Demographic information (age, race, gender, and ethnicity);
- Reason for screening failure.

### **Randomization**

Randomization will occur if the patient meets all inclusion criteria and does not meet any exclusion criteria.

Each case will be randomized to one of two groups in a 1:1 ratio. The only difference between the groups will be the suturing material and technique. The plan is to randomize at least 92 subjects for each of the two groups. A central randomization will be used in this study so that the study team cannot guess the upcoming assigned group.

#### **3.4.1 Visit 1 – Screening/Baseline Visit**

The following screening activities will occur prior to the study procedure (performed within 30 days of surgery):

- The subject must be given ample time to review and sign the ICD;
- Collection of demographic information (year of birth, race, gender, ethnicity, education, occupation);
- Review and collection of medical/surgical history
- Review/collection of inclusion/exclusion criteria and determination as to whether the subject is eligible for participation (retrospective data, per site SOC, is permitted to determine eligibility);
- Urine/blood pregnancy test;
- Date of hospital admission;
- Knee Pain VAS
- EQ-5D-3L
- Physical Examination, including height, weight and ROM of knee; and
- Concomitant medications (including pain and antibiotics) from the admission;

#### **3.4.2 Visit 2 – Randomization**

The following must be obtained prior to the surgical procedure:

- Interactive web response system/ interactive voice response system
- Confirm inclusion and exclusion criteria
- Concomitant medications including pain and antibiotics

#### **3.4.3 Visit 3 – Surgical Procedure**

##### **3.4.3.1 Pre-procedure**

The following must be obtained prior to the surgical procedure:

- Update to medical/surgical/ history
- Concomitant medications including pain and antibiotics

### **3.4.3.2 Intraoperative**

Data collected during procedure:

- Procedure time:
  - The time in minutes and seconds by a calibrated stopwatch between placement of the first suture throws in the deep tissue to the completion of intradermal layer closure. Total operation time: defined as the time in minutes beginning with first incision to skin closure.
- Overall operating room (OR) time: defined as the time in minutes from anesthesia to exiting the OR;
- Device usage data
- The code and quantity of wound closure device, including suture and TSA
- Operating room resource utilization;
- Intra-operative device failure rates;
- Anesthesia method;
- Wound Complication Assessment;
- Concomitant medications including pain and antibiotics (except for anesthesia medications)..;
- Adverse Events (Concomitant medication usage associated with AEs will also be captured)

### **3.4.4 Visit 4 – Post-Op through Discharge**

The following must be obtained in this visit.

- Knee pain VAS
- ROM
- EQ-5D-3L
- Concomitant medications including pain and antibiotics
- Wound Complication Assessment
- Adverse Events (Concomitant medication usage associated with AEs will also be captured)
- SSI
- AIRE
- Length of stay: defined as time between procedure and discharge.
- Health Economic Data Collection

### **3.4.5 Visit 5 – 30-42 Days**

Between 30 and 42 days post procedure; the following must be conducted/obtained:

- Knee pain VAS
- ROM
- EQ-5D-3L
- Concomitant medications including pain and antibiotics
- Wound Complication Assessment

- Adverse Events (Concomitant medication usage associated with AEs will also be captured)
- SSI
- AIRE

## 4.0 Data Management and Integrity

### 4.1 Data Completion and Record Keeping

#### 4.1.1 Source Documents

Source documents are documents on which information regarding subjects is first recorded, including printed, optical, or electronic documents. Investigator subject files or hospital records generally are the basis of source document information. This includes but is not limited to, original subject files; hospital/clinic records; original recordings /tracing; digital images from automated instruments; radiographs; device accountability records; photographic negatives; and records kept at the investigation site, at the laboratories and at other departments involved in the clinical investigation.

Source documents must be retained by the Investigator as part of the subject's permanent medical record. The information in the source documents is used to complete the eCRFs. All information captured on the eCRFs should be completely and accurately supported in source documentation. Any additional information relevant to the study should be included in the source documents. In particular, any deviations from the study protocol or procedures should be recorded in the source documents. The Investigator will retain originals of all source documents, subject consent forms, and study data.

#### 4.1.2 Electronic Data Capture

An electronic data capture (EDC) system will be utilized by study site personnel to transfer study data from source records (medical records and/or source document worksheets) onto common eCRFs. This system is a web-based, secure electronic software application (Medidata® Rave, [name]). This system was designed and is developed and maintained by Medidata in a manner that is compliant with national and international GCP data protection/data privacy and electronic record/electronic signature (e.g., 21 CFR Part 11) regulatory requirements. The EDC system will be used to facilitate the collection of all study data at the site. Designated site personnel will be responsible for entering patient data into the EDC system. All external and Sponsor internal users will be trained on the EDC application at a level dependent on their planned function. An EDC digital User Manual will be available under the help menu within the Medidata® Rave website to assist in the collection and entry of source data into the electronic casebook.

A 24/7/365 Help Desk Support line (per Medidata web site) staffed by the outsourced vendor will also be available to respond to site-monitor questions.

#### 4.1.3 Data Collection

Each EDC eCRF will be completed by the PI or PI's designee. Every effort should be made to respond to all monitoring and/or data management questions on each eCRF as completion of the data is required by the protocol. A unique ID number will identify each subject. The subject's unique ID number will be visible on each eCRF. At no time should the subject name appear on the eCRFs.

All data should be recorded accurately and completely. The Investigator is responsible for reviewing and approving each completed eCRF. Assurance of overall review and approval

will be documented by the Investigator electronically signing each subject's electronic casebook.

#### **4.1.4 Data Correction**

Required data corrections to eCRFs will be prompted via automated electronic edit checks and/or queries manually created by Sponsor reviewers. The change(s), individual making the change(s), and time the change(s) were made to the eCRFs will be automatically captured in the audit trail within Medidata® Rave.

#### **4.1.5 Data Privacy**

The collection, use, and disclosure of all personal data, including subject health and medical information, are to be maintained in compliance with applicable personal data protection and security laws and regulations that govern protected health information and the informed consent given by each study subject. When collecting and processing such personal data, appropriate measures are to be taken to maintain the confidentiality of patient health and medical information and to prevent access by unauthorized persons.

#### **4.1.6 Record Retention, Inspection, and Custody**

The PI must maintain all documentation related to the study for at least ten years after site closure (per applicable local regulation) and until they receive Sponsor notification. The PI will allow representatives of the Sponsor, the China Food and Drug Administration (CFDA), or other government regulatory agencies to inspect all study records, eCRFs, and corresponding portions of the subject's office and/or hospital medical records at regular intervals during the study. These inspections are to verify adherence to the protocol, integrity of the data being captured on the eCRFs, and compliance with applicable regulations.

Subject medical records will be maintained in a confidential manner. Study reports will not identify subjects by name.

If custody of the records is transferred, notice of such a transfer should be given to the Sponsor no later than 10 working days after the transfer occurs.

### **4.2 Medical Dictionary Coding**

Medical dictionary coding of verbatim AE, Serious Adverse Event (SAE), and concomitant prescription medications terms captured on eCRFs will be performed using a coding thesaurus algorithm. The Medical Dictionary for Regulatory Activities and World Health Organization Drug Dictionary will be used after data entry and query resolution, via auto-encoding and interactive coding processes.

### **4.3 Data Quality Assurance**

Steps to be taken to assure the accuracy and reliability of data include the selection of qualified investigators and appropriate study centers, review of protocol procedures with the Investigator and associated personnel prior to the study, and periodic monitoring visits by the Sponsor. The Sponsor will review eCRF's for accuracy and completeness during on-site monitoring visits and after their return to the Sponsor; any discrepancies will be resolved with the Investigator or designees, as appropriate. The data will be entered into the clinical study database and verified for accuracy.

#### **4.3.1 Monitoring**

This study will be monitored by the Sponsor to ensure:

- The rights and well-being of the subjects are protected;
- Reported study data is accurate, complete, and verifiable from source documents; and
- The conduct of the study is in compliance with the currently approved protocol/amendment(s), and with applicable local regulatory requirements.

The extent and nature of monitoring will be predetermined and based on considerations such as the objective, design, complexity, and endpoints of the study and mutually agreed to by the Sponsor and investigators. Monitors will comply with established written standard operating procedures as well as procedures (i.e., monitoring plan) specified by the Sponsor for monitoring this study. These monitoring procedures are characterized in the monitoring plan for this study.

#### **4.3.2 Regulatory Requirements**

This study will be conducted in accordance with ICH Harmonized Tripartite Guideline for Good Clinical Practice (1996), the Declaration of Helsinki (2008), as well as any other applicable local regulatory requirements.

### **4.4 Protocol Deviations**

A deviation (any activity conducted outside the parameters established by the study protocol) can be identified from a number of sources. Potential sources include, but are not limited to: a member of the Investigator's staff, a Sponsor representative during monitoring visits, or a member of the data management or statistical groups when entering or analyzing data. Regardless of the source, it is crucial to document the deviation. The PI will report protocol deviations to the IRB as required by the IRB procedures.

### **4.5 Statistical Methods Planned in the Protocol and Determination of Sample Sizes**

#### **4.5.1 Statistical and Analytical Plans**

The Data Management and Biostatistics groups of Global Surgery Clinical Development will be responsible for the analysis of data from this protocol. A comprehensive and detailed Statistical Analysis Plan (SAP) will be finalized prior to database lock and will supplement the statistical design and analysis described in this section.

#### **4.5.2 Determination of Sample Size**

The proposed sample size of 92 patients per arm (184 total) is considered adequate to test the hypothesis that [REDACTED] can reduce the time for incision closure compared to conventional sutures. Based upon a review of the literature, the mean incision closure time was assumed to be [REDACTED] minutes for conventional sutures, being calculated as a weighted (based on number of subjects) mean of the means observed in the studies reviewed. The studies reported incision closure times ranging between 14.4 to 26.5 minutes [5, 7-10]. It is expected that the [REDACTED] can reduce the incision closure time by [REDACTED] % compared to conventional sutures; therefore, the assumed mean closure time for [REDACTED] is [REDACTED] minutes. The standard deviations observed in the reviewed literature range from 3.43 to 8.5 minutes for the conventional sutures; the standard deviation for this study was conservatively assumed to be [REDACTED] minutes in both groups for several

reasons, such as the lack of data for [REDACTED] and that this patient sample may be older and with larger BMI. The distribution of incision closure time is assumed to be normal.

The statistical hypotheses for the primary endpoint are as follows:

- H0: Mean Barbed  $\geq$  Mean conventional suture tested against the alternative hypothesis
- Ha: Mean Barbed  $<$  Mean conventional suture;

Where:

- The assumed mean time to incision closure in conventional group is [REDACTED] minutes;
- The mean time to closure in [REDACTED] is [REDACTED] minutes;
- The assumed standard deviations in the two groups are both 8.

Based upon these assumptions, a total seventy seven (77) evaluable subjects per arm will achieve 90% power to detect a difference of [REDACTED] minutes (expected mean for [REDACTED] of [REDACTED] minutes and the conventional group of [REDACTED] minutes) with estimated group standard deviations of [REDACTED] using a one-sided two-sample t-test. The assumed one-sided significance level is 0.025.

If the higher limit of the one-sided 97.5% confidence interval for the difference in the Mean [REDACTED] time minus the Mean closure time for conventional suture is smaller than 0, then it will be concluded that [REDACTED] is considered to be superior to conventional suture. The sample size is adjusted to 92 per arm to account for a 16% withdraw rate [25-28].

#### 4.5.3 Analysis Sets

There will be three analysis sets defined:

- Modified Intent-to-treat set (mITT set) consists of all randomized subjects who had the surgical incisions closed using the randomized suture
- Evaluable [or Per-Protocol (PP)] set consists of all mITT subjects who have no major protocol violations.
- Safety set consists of all subjects who receive surgery.

Major protocol deviations are deviations that have an impact on the primary endpoint, or that have an impact on the randomization assignment. These will be determined prior to database lock.

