Statistical Methods:	
All efficacy endpoints will be summarized descriptively by treatment group. The continuous variables will be summarized descriptively by number of subjects, mean, standard deviation, minimum, and maximum. Categorical data will be summarized descriptively by frequencies along with the associated percentages.
 
In addition, for the primary efficacy endpoint, a one-sided 97.5% confidence interval for the difference in treatment group means (Mean [REDACTED] closure time minus the Mean closure time for conventional suture) will be constructed using the t-distribution.
 
The primary efficacy endpoint will be analyzed using the mITT and Per-Protocol analysis sets. The ITT analysis will be considered as the primary analysis. All secondary efficacy endpoints will be analyzed using the mITT analysis set.
 
All secondary safety endpoints will be summarized descriptively by treatment group for the Safety analysis set using available data. The continuous variables will be summarized descriptively by number of subjects, mean, standard deviation, minimum, and maximum. Categorical data will be summarized descriptively by frequencies along with the associated percentages. No inferential statistics will be generated for the secondary safety endpoints.

-----------------------------	---

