#### **Other**

- Either deep or intermediate layer can't be closed by one [REDACTED] suture;
- PI believed the incision is not suitable to be closed by absorbable suture (e.g., the tissue where prolonged (beyond six weeks) approximation of tissue under stress is required).

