#### 4.5.4 Analysis of Primary and Secondary Efficacy Endpoints

For the primary efficacy endpoint, a one-sided 97.5% confidence interval for the difference in treatment group means (Mean [REDACTED] closure time *minus* the Mean closure time for conventional suture) will be constructed using the t-distribution. If the higher limit of the confidence interval is smaller than 0, then it will be concluded that [REDACTED] is considered to be superior to conventional suture.

The primary efficacy endpoint will be analyzed using the mITT and Per-Protocol analysis sets. The mITT analysis will be considered primary analysis. All secondary efficacy endpoints will be analyzed using the mITT analysis set.

All efficacy endpoints (see section 2.1) will be summarized descriptively by treatment group. The continuous variables will be summarized descriptively by number of subjects, mean, standard

deviation, minimum, and maximum. Categorical data will be summarized descriptively by frequencies along with the associated percentages. No inferential statistics will be generated for the secondary efficacy endpoints.

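### The primary mITT set drops randomized subjects not closed with the assigned suture, and no planned efficacy analysis keeps all operated subjects as randomized

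*Protocol*

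**What the plan says.** Protocol 4.5.3 and SAP 2.2 define the mITT set identically, as "all randomized subjects who had the surgical incisions closed using the randomized suture". The per-protocol set "consists of all mITT subjects who have no major protocol violations". The third set, Safety, holds every operated subject but is assigned only to safety endpoints (protocol 4.5.5, SAP 3.3).

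Protocol 4.5.4 and SAP 3.2.1.1 analyse the primary endpoint on mITT and per-protocol, and add: "The mITT analysis will be considered primary analysis". Secondary efficacy uses mITT. The Synopsis says instead: "The ITT analysis will be considered as the primary analysis". Neither document defines an ITT set, and the Synopsis sentence just before that one names only mITT and per-protocol.

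Three other places bear on who is excluded:

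- Protocol 3.3.2, on the surgeon: "It is not possible to blind the implanting physician due to the different suturing technique and products".
- Protocol 3.2.3, Other, lists as a withdrawal reason: "Either deep or intermediate layer can't be closed by one" unit of a named suture (name redacted). A second reason, an incision unsuitable for absorbable suture, names no arm.
- Protocol 3.3.1 says that in the barbed arm "the deep layer and the intermediate layer will be repaired and closed by using one" suture for each layer. It sets no such limit for the control arm.

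**The concern.** Membership of the primary set depends on what happens between the first deep throw and the end of the intradermal layer, which is exactly the period the primary endpoint times. A difficult closure can therefore both lengthen the outcome and remove the subject. The person who decides knows the assignment.

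The 3.2.3 reason about one suture per layer, read with 3.3.1, probably acts on the barbed arm only. Because the product name is redacted, this is an inference. The plan also does not say whether such a subject stays in mITT: a layer closed with two sutures of the assigned type may still qualify.

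At stake is a superiority rule (upper 97.5% limit below 0) applied to groups that randomization no longer fully protects. If the excluded closures are long and mainly barbed, the claimed saving is too large and the error rate exceeds 2.5%. Planned tables would let a reader derive how many subjects were excluded per arm, but not what the result would be with them included.

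**Working it through.** **1. The plan's own figures.** Inputs from protocol 4.5.2: 77 evaluable per arm, 90% power, one-sided 0.025, SD 8, 16% withdrawal. Then 77 / 0.84 = 91.7, so 92 per arm, which agrees with the plan. The allowance is 92 − 77 = 15 per arm. The design difference is redacted. Solving the noncentral t for n = 77, SD 8 and power 0.90 gives 4.206 min, or 4.206 / 16.89 = 24.9% of the control mean in SAP 1.3.3. At 92 per arm, power for 4.206 min is 94.4%.

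**2. Where a subject not closed with the assigned suture appears.**

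| Analysis | Set | Included? |
|---|---|---|
| Primary endpoint, primary analysis | mITT | No |
| Primary endpoint, second analysis | Per-protocol (within mITT) | No |
| Secondary efficacy | mITT | No |
| Sensitivity or exploratory | None defined (SAP 2.4 only alludes to them; SAP 3.4 has none) | No |
| Safety endpoints | Safety | Yes |

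**3. Illustrated bias.** The documents give neither an exclusion rate nor its link with closure time, so both are assumed. Closure times are normal with SD 8, there are 92 per arm and no true difference. The k subjects highest on a latent difficulty factor, correlated rho with closure time, are removed. A pooled one-sided t-test at 0.025 follows (400,000 simulated trials per scenario).

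Apparent saving = rho × 8 × k × m / (92 − k), where m is the expected mean of the top k of 92 standard normal values: m = 2.296 for k = 2 and 1.983 for k = 5.

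- k = 2, rho 0.3: 0.3 × 8 × 2 × 2.296 / 90 = 0.122 min; rho 0.5: 0.204 min.
- k = 5, rho 0.3: 0.3 × 8 × 5 × 1.983 / 87 = 0.274 min; rho 0.5: 0.456 min.
- 5 barbed and 2 control: 0.274 − 0.122 ≈ 0.151 min (unrounded inputs); 0.456 − 0.204 = 0.252 min.

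| Excluded (barbed / control) | Error, rho 0 | rho 0.3 | rho 0.5 | Saving, rho 0.3 to 0.5 (min) |
|---|---|---|---|---|
| 2 / 0 | 2.5% | 3.2% | 3.8% | 0.12 to 0.20 |
| 5 / 0 | 2.5% | 4.2% | 5.9% | 0.27 to 0.46 |
| 5 / 2 | 2.5% | 3.4% | 4.3% | 0.15 to 0.25 |
| 5 / 5 | 2.5% | 2.5% | 2.7% | about 0 |

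Relative to the inferred design difference, the barbed-only savings run from 0.122 / 4.206 = 2.9% to 0.456 / 4.206 = 10.8%.

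**4. What rho means in minutes.** Excluded closures exceed retained ones in the same arm by rho × 8 × m × 92 / (92 − k). For k = 5 this is 0.3 × 8 × 1.983 × 92 / 87 = 5.0 min, and 8.4 min at rho 0.5.

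**5. Cross-check by a simpler route.** If a share f of the barbed arm is excluded and those closures are x min longer than the retained ones, the bias is f × x. For f = 5%: x = 5 gives 0.25 min and error 4.0%; x = 10 gives 0.5 min and 6.1%. This agrees with step 3. For f = 10% and x = 10, the bias is 1.0 min and the error 12.7%, but nothing in the documents supports a rate that high.

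**6. If the planned effect is real.** With a true 4.206 min difference, power is 94.4% with no exclusion, 95.4% to 96.0% with 2 barbed-only exclusions and 96.2% to 97.4% with 5 (rho 0.3 to 0.5; 100,000 trials each).

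**The case against.** The case for leaving the plan alone has several parts.

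- *The route to one-sided exclusion is undocumented.* The one-suture reason is a withdrawal reason, not an mITT exclusion. A layer closed with two assigned sutures may meet the mITT wording, and 3.2.3 says data collected before withdrawal are still considered. This stands as far as it goes: the direction is conditional. But 3.2.3 names no analysis set, and any subject switched to another material still leaves mITT.
- *The size is assumed.* This is correct. At rho 0.1 the error is only 2.7% (k = 2) or 3.0% (k = 5), with savings of 0.04 and 0.09 min. The 15-per-arm allowance is for withdrawal, and the plan does not say how much of it would be mITT exclusion.
- *Exclusion may be rare.* The 15 cm incision length and the 1:3 ratio of incision to suture length may keep it so, but both are only recommendations.
- *Reporting is already planned.* Randomized numbers by arm (SAP 3.1.1), baseline tables by arm for all enrolled and for mITT (SAP 3.1.3) and n (missing) by arm (SAP 3.2.1.1) let exclusion counts be derived. SAP 3.1.1 also summarises reasons for early termination. It does not say by arm, and it misses non-use of the assigned suture without withdrawal. The by-arm deviation table in SAP 3.1.2 is confined to mITT, so excluded subjects appear only in the listing. The table shells are a separate document and cannot be checked.
- *mITT fits an objective about closure using each suture.* This is arguable, and it is why a pre-specified sensitivity analysis is an acceptable minimum.

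**Conclusion.** The concern holds. Followed exactly, the plan tests superiority in a set selected after randomization by an unblinded surgeon, and no defined efficacy analysis restores the excluded subjects. The undefined ITT label in the Synopsis does not fill the gap and conflicts with protocol 4.5.4 and the SAP.

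The size cannot be known from the documents. Under the stated assumptions, 2 to 5 barbed-only exclusions give an error of 3.2% to 5.9% instead of 2.5% and overstate the saving by 0.12 to 0.46 min. With balanced exclusion, or exclusion unrelated to closure time, there is little or no bias. If the true saving is near 4.2 min, the conclusion would seldom change. The concern is mainly the size of the claimed saving, and error control when the true effect is small or absent. This should be fixed; confidence is medium because the rate, arm and closure times of exclusions are unknown.

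**What to change.** 1. In the Synopsis, protocol 4.5.3 and 4.5.4, and SAP 2.2 and 3.2.1.1, define the primary set as all randomized subjects who undergo surgery, analysed in the assigned arm whatever suture was finally used. Use one name for it throughout, replacing ITT in the Synopsis. Keep the present mITT set as supportive, and state whether a layer closed with more than one assigned suture belongs to it. If the present set stays primary, pre-specify the as-randomized analysis at least as a sensitivity analysis.
2. Protocol 3.4.3.2 already requires timing "by a calibrated stopwatch between placement of the first suture throws in the deep tissue to the completion of intradermal layer closure". Add a sentence that this also applies when a 3.2.3 Other reason arises during closure, and that time for any extra or substitute suture counts.
3. Tabulate by arm, for all randomized subjects, non-use of the assigned suture and 3.2.3 Other withdrawals, with reasons.

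The withdrawal text in 3.2.3 and the analysis-set definitions must be reconciled; no clinical rule is proposed here.

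The cost is wording, one table and one clarifying sentence. Stopwatch time and device code and quantity are already recorded, so no new subjects, visits or data fields are needed. The downside is a somewhat smaller and more variable observed saving. For example, take a difference of 4.22 min (25% of 16.89) among retained subjects, with 5% of barbed closures excluded and 10 min longer. The as-randomized difference is then 4.22 − 0.05 × 10 = 3.72 min, with power of about 87% at 92 per arm. At 2% and 5 min it is 4.12 min and about 94%.
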